11.14 Appendix 14. Modified Toxicity Probability Interval Design

A modified Toxicity Probability Interval (mTPI) design will be used to guide dose exploration. The OBD/MSBED is defined as the minimum safe and biologically effective combination dose with a probability of DLT lower than or close to a targeted toxicity probability of 0.2. The doses are considered close to the OBD if the toxicity probabilities belong to the proper dosing interval (0.25, 0.35) which corresponds to staying at the current dose (S). The underdosing interval is defined as (0, 0.25) in which the doses are deemed lower than the OBD and corresponds to a dose escalation (E). The overdosing interval is (0.35, 1) in which the doses are deemed higher than the OBD and corresponds to a dose de-escalation (D).

The dose-finding decisions are guided based on Bayesian decision rule by minimizing the posterior expected loss through calculating the Unit Probability Mass (UPM). At each dose level, the UPM is computed for the dosing intervals using the observed data enrolled at current dose. The dose-finding decision is determined as the interval with maximum UPM. A set of independent and non-informative prior Beta (1,1) is used for each dose level, which provides equal prior expected loss for the decisions (Ji et al, 2010). Dose escalation will not occur unless at least 6 subjects are treated at the current dose level. In addition, any dose whose posterior probability of toxicity is greater than the target toxicity exceeds 80% will be considered as unacceptable toxicity. This dose and higher doses will not be used again in the trial. Dose exploration will continue until either the maximum number of subjects (up to 30 subjects in monotherapy part and up to 30 subjects in combination therapy part) are treated or all doses are determined to be intolerable.

Protocol Number: 20200392

Date: 11 April 2022 Page 1 of 12

Amendment 3

Protocol Title: A Phase 1 Study of AMG 176 as Monotherapy and in Combination with Azacitidine in Higher-Risk Myelodysplastic Syndrome and Chronic Myelomonocytic Leukemia

Amgen Protocol Number AMG 176 20200392

Amendment Date: 11 April 2022

Rationale:

The protocol has been amended to incorporate minor changes based on the need to replace the assay used to evaluate troponin-I elevations with a new high-sensitivity assay. The current cardiac monitoring plan for AMG 176 employs testing of troponin-I with Troponin-I Ultra assay for all screening, grading, and withholding decisions. The manufacturer has decided to retire Troponin-I Ultra assay effective on end of year 2021 due to low tolerance and sensitivity issues and has recommended to transition to High-Sensitivity Troponin-I (TNIH) assay. Both assays use the ADVIA Centaur XP system which is specified on the study protocol. An assay verification study was conducted at Q2 laboratory to evaluate the accuracy and clinical performance of the new High-Sensitivity Troponin-I (TNIH) assay and to compare it to Troponin-I Ultra assay. The comparison report demonstrated consistency between the two assays and support the replacement of Troponin-I Ultra assay with High-Sensitivity Troponin-I (TNIH) assay. Based on the acceptable correlation data and the urgent need for continued cardiac monitoring, Amgen requested to replace Troponin-I Ultra assay with the new High-Sensitivity Troponin-I (TNIH) assay and continue to use the current grading criteria with the exception of increasing the male 99th percentile upper reference limit (URL) to 0.059 ng/mL per manufacturer's guideline. Since the protocol only refers to the system (ADVIA Centaur XP system) used to perform the troponin-I assay and not to the specific name of the assay, the only update made to the protocol relates to increasing the male 99th percentile URL to 0.059 ng/mL and maintaining the URL of 0.04 ng/mL for

Protocol Number: 20200392

Date: 11 April 2022 Page 2 of 12

females in relevant sections of the protocol. Minor changes were also made to clarify/correct other items in the protocol.

Changes include:

- Update to inclusion criterion #103 to separate the note for clarity.
- Update to inclusion criterion #104 to remove prior cohort completion and data review by FDA since the statement does not define eligibility, and to separate the note.
- Update exclusion criterion #214 to reduce COVID-19 vaccination time point prior to dosing from 28 days to 14 days.
- A clarification to remove biomarker from central lab testing was made to the schedule of activities (section 1.3) as the standard of care would be performed by the local laboratory.
- Remove reference to central testing of troponin-I with high sensitivity
 Abbott ARCHITECT assay used for exploratory purposes to evaluate biological variations of troponin-I in oncology subjects (section 6.2.2.2.5) and (section 11.10.1).
- Update to grading of troponin-I elevation (section 6.2.2.2.5) and (section 11.10.1) to align female and male requirements with assay manufacturer guidelines.
- Update to Uniform Response Criteria for Myelodysplastic/Myeloproliferative Neoplasm (section 11.12) to clarify the definition of progression and relapse
- Administration, typographical, and formatting changes were made throughout the protocol.

Protocol Number: 20200392 Date: 14 February 2022

Amendment 2

Page 1 of 1

Protocol Title: A Phase 1 Study of AMG 176 as Monotherapy and in Combination with Azacitidine in Higher-Risk Myelodysplastic Syndrome and Chronic Myelomonocytic Leukemia

Amgen Protocol Number AMG 176 20200392

EudraCT number: TBD

NCT Number: TBD

Amendment Date: 14 February 2022

Rationale:

This protocol is being amended to include changes as described in Amgen's response to the Food and Drug Administration (FDA) potential hold comments and deficiencies received on 19 November 2021. Changes include the following:

- Addition of a 240 mg/m² dose level to Part 1A and Part 1B.
- Minor formatting, administrative, and typographical edits.

Protocol Number: 20200392

Date: 25 October 2021 Page 1 of 2

Amendment 1

Protocol Title: A Phase 1 Study of AMG 176 as Monotherapy and in Combination with Azacitidine in Higher-Risk Myelodysplastic Syndrome and Chronic Myelomonocytic Leukemia

Amgen Protocol Number AMG 176 20200392

EudraCT number: TBD

NCT Number: TBD

Amendment Date: 25 October 2021

Rationale:

This protocol is being amended to include changes as described in Amgen's response to the Food and Drug Administration (FDA) potential hold comments and deficiencies received on 06 October 2021. Additionally, required safety template language was added in Section 8.4.6. Changes include the following:

- Revision of dose-limiting toxicity (DLT) criteria as per FDA's recommendations, specifically cardiac DLTs, hematologic DLTs, and DLTs related to tumor lysis syndrome (TLS).
- Revision of the targeted toxicity probability to 0.2 as well as revision of the modified
 Toxicity Probability Interval (mTPI) based guidelines for dose level decisions.
- Revision of dose expansion stopping rules.
- Revision of the protocol to indicate the primary objective is to find the Optimal Biological Dose (OBD), rather than the maximum tolerated dose (MTD), escalating to the Minimum Safe and Biologically Effective Dose (MSBED).
- Clarified the number of dose reductions a subject is eligible for.

Protocol Number: 20200392

Date: 25 October 2021 Page 2 of 2

 Revision of protocol Section 2.2.2.4, AMG 176 Clinical Experience, to summarize the available data from the ongoing Study 20150161, Part 4, for AMG 176 (60 and 120 mg/m² dose) in combination with azacitidine.

- Revision throughout the protocol to clarify that subjects will not be enrolled into the "Newly Diagnosed" cohort in Part 2 until all previous cohorts have been completed and the data reviewed by the FDA.
- Revision of the response criteria to utilize the Uniform Response Criteria for Myelodysplastic/Myeloproliferative Neoplasms (MDS/MPN) as included in Appendix 12 of the protocol.
- Revision to Section 4.1.2 to clarify that subjects may remain on treatment with either or both AMG 176 and azacytidine as long as, in the opinion of the investigator, the subject continues to derive clinical benefit and has otherwise not had an event requiring permanent discontinuation.
- Revision to remove the enrollment requirement of blast count of ≥ 5% in patients who
 are otherwise eligible.
- Revision to include required template safety reporting language in Section 8.4.6.
- Administrative, typographical, and formatting changes throughout the protocol.

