4.1 Overall Design

This study is a phase 1 clinical trial designed to assess the safety, tolerability, and efficacy of AMG 176 in combination with the 7-day regimen of azacitidine for the treatment of HR-MDS/CMML. Subjects will be treated with IV AMG 176 and IV or SC azacitidine. The study consists of 2 parts.

4.1.1 Part 1 – Dose Escalation/Determination of Optimal Biological Dose (OBD) and Minimal Safe and Biologically Effective Dose (MSBED)

In Part 1, the modified Toxicity Probability Interval (mTPI) design will be applied for dose escalation. Three dose levels of AMG 176 monotherapy will first be tested, and after the OBD is found, three dose levels of AMG 176 in combination with azacitidine will be tested.

After obtaining the monotherapy data from Part 1A, available data for monotherapy and combination therapy (with azacitidine) from the FIH study (Study 20150161) will also be leveraged to identify the MSBED for AMG 176. Dose exploration for AMG 176 in combination with azacitidine in Part 1B will then begin at the monotherapy MSBED -1 for AMG 176. The combination MSBED in Part 1B will be selected after an integrated assessment of all available clinical safety, efficacy, PK, and pharmacodynamic (PD) data for AMG 176 is performed, in order to select doses of AMG 176 that are likely to achieve the optimal benefit-risk profile.

Protocol Number: 20200392

Date: 28 April 2022 Page 41 of 149

Each dose cohort will initially enroll 3 to 4 subjects and up to 10 subjects per cohort may be enrolled. After reviewing all available safety data, dose level decisions (eg, escalation, de-escalation) will be made by the DLRT using mTPI model (Ji et al, 2010) based on all subjects that have been enrolled at the current dose. The DLRT may change the dose/dosing scheduled based on emerging data. The OBD/MSBED is defined as the minimum safe and biologically effective combination dose with a probability of DLT lower than or close to a targeted toxicity probability of 0.2.

Dose escalation is considered complete if one of the following rules is met:

 The highest planned dose level is evaluated, OBD has not been defined, and no DLTs occur at any dose level. In this case, the Maximum Administered Dose (MAD) may be used for Part 2.

2. An OBD is identified.

Guidelines for dose level decisions can be found in Table 4-1. Details regarding the mTPI model are described in Appendix 14 (see Section 11.14).

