Number of DLTs No. of DLT-evaluable^a subjects treated at current dose Escalate Stay at current dose De-escalate^b 0 1 3 ≥ **2** 6 0-1 ≥ 2 9 0-1 2 ≥ 3 10^c 0-1 2-3 ≥ 4

Table 4-1. Guidelines for Dose Level Decisions in Part 1

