### Part 1 – Dose Escalation/Determination of Optimal Biological Dose (OBD) and Minimum Safe and Biologically Effective Dose (MSBED)

In Part 1, the modified Toxicity Probability Interval (mTPI) design will be applied for dose escalation.

Three dose levels of AMG 176 monotherapy will first be tested in Part 1A, and after the OBD or MSBED is found, three dose levels of AMG 176 in combination with azacitidine will be tested in Part 1B.

Each dose cohort will initially enroll 3 to 4 subjects and up to 10 subjects per cohort may be enrolled. After reviewing all available safety data, dose level recommendations (eg, escalation, de-escalation) will be made by the Dose Level Review Team (DLRT) using an mTPI model (Ji et al, 2010) based on all subjects that have been enrolled at the current dose. The DLRT may change the dose/dosing scheduled based on emerging data. The OBD/MSBED is defined as the minimum safe and biologically effective combination dose with a probability of DLT lower than or close to a targeted toxicity probability of 0.2.

Dose escalation is considered complete if one of the following rules is met:

- 1. The highest planned dose level is evaluated, OBD has not been defined, and no DLTs occur at any dose level. In this case, the Maximum Administered Dose (MAD) may be used for Part 2.
- 2. An OBD is identified.

Guidelines for dose level decisions can be found in Table 3-1. Details regarding the mTPI model are described in Appendix B.

Table 3-1. Guidelines for Dose Level Decisions in Part 1

	Number of DLTs		
No. of DLT-evaluable a subjects treated at current dose	Escalate	Stay at current dose	De-escalate b
3	0	1	≥ 2
6	0-1	-	≥ 2
9	0-1	2	≥ 3

Protocol Number: 20200392

Date: 10 May 2024 Page 14 of 33

	Number of DLTs		
No. of DLT-evaluable a subjects treated at current dose	Escalate	Stay at current dose	De-escalate b
10°	0-1	2-3	≥ 4

DLT = dose limiting toxicity.

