#### 10. Changes From Protocol-specified Analyses

During the initial development of this document, it was realized that there are protocolspecified analyses that cannot be implemented/performed and the protocol is not required to be amended. Following changes are required-

- Though protocol states that the Uniform Response criteria were used for deriving the responses; however, International Working Group MDS Response Criteria (2006) (Appendix E) were used to classify responses for patients with MDS (based on NCCN guidelines Jan 2024). No patients with CMML were enrolled.
- Tables based on the primary analysis endpoints and secondary endpoints will not be generated due to the limited number of subjects and early close out of the study.
   These changes will also be documented in the Clinical Study Report.

Primary endpoints will not be analyzed using tables; however, listings will be provided only for clinical laboratory tests, vital signs, ECG, and adverse events including DLTs, treatment-related and treatment-emergent adverse events.

 Part 1A – QW Monotherapy (Dose Exploration)- Incidence of dose limiting toxicities (DLTs), treatment-related, treatment-emergent adverse events and clinically significant changes in vital signs, electrocardiogram (ECGs), and clinical laboratory tests.

No analysis will be performed for below secondary endpoints:

- Part 1B QW Combination Therapy (Dose Exploration) Overall response according to the IWG-MDS Response criteria for MDS/MPN (2006), EFS, time to response, and DOR
- 2. Part 2 QW Combination Therapy (Dose Expansion)
  - a. Time to transformation to Acute Myeloid Leukemia (AML)
  - b. Duration of Response (DOR)
  - c. Overall Survival (OS)
  - d. Time to Next MDS Treatment (TTNT)
  - e. EFS

Protocol Number: 20200392

Date: 10 May 2024 Page 24 of 33

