#### Appendix B. Modified Toxicity Probability Interval Design

A modified Toxicity Probability Interval (mTPI) design will be used to guide dose exploration. The OBD/MSBED is defined as the minimum safe and biologically effective combination dose with a probability of DLT lower than or close to a targeted toxicity probability of 0.2. The doses are considered close to the OBD if the toxicity probabilities belong to the proper dosing interval (0.25, 0.35) which corresponds to staying at the current dose (S). The underdosing interval is defined as (0, 0.25) in which the doses are deemed lower than the OBD and corresponds to a dose escalation (E). The overdosing interval is (0.35, 1) in which the doses are deemed higher than the OBD and corresponds to a dose de-escalation (D).

The dose-finding decisions are guided based on Bayesian decision rule by minimizing the posterior expected loss through calculating the Unit Probability Mass (UPM). At each dose level, the UPM is computed for the dosing intervals using the observed data enrolled at current dose. The dose-finding decision is determined as the interval with maximum UPM. A set of independent and non-informative prior Beta (1,1) is used for each dose level, which provides equal prior expected loss for the decisions (Ji et al, 2010). Dose escalation will not occur unless at least 6 subjects are treated at the current dose level. In addition, any dose whose posterior probability of toxicity is greater than the target toxicity exceeds 80% will be considered as unacceptable toxicity. This dose and higher doses will not be used again in the trial. Dose exploration will continue until either the maximum number of subjects (up to 30 subjects in monotherapy part and up to 30 subjects in combination therapy part) are treated or all doses are determined to be intolerable.

Protocol Number: 20200392

Date: 10 May 2024 Page 29 of 33

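### The mTPI stay interval (0.25, 0.35) leaves out the 0.2 DLT target, so a dose at the target counts as underdosed and 1 DLT in 6 means escalate instead of stay

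*Protocol*

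**What the plan says.** Protocol Section 4.1.1 defines the OBD/MSBED as a safe and biologically effective dose "with a probability of DLT lower than or close to a targeted toxicity probability of 0.2". Protocol Appendix 14 repeats that target. It then says "The doses are considered close to the OBD if the toxicity probabilities belong to the proper dosing interval (0.25, 0.35"), which means stay. Doses in (0.35, 1) are overdosing, which means de-escalate. SAP Appendix B carries the same text: "The underdosing interval is defined as (0, 0.25) in which the doses are deemed lower than the OBD", which means escalate.

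The prior is Beta(1,1), and the decision goes to the interval with the largest unit probability mass (UPM). Two further rules apply. No escalation is allowed before 6 subjects are treated at the dose, and "any dose whose posterior probability of toxicity is greater than the target toxicity exceeds 80% will be considered as unacceptable toxicity".

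The decisions are tabulated in Protocol "Table 4-1. Guidelines for Dose Level Decisions in Part 1" and again in SAP Table 3-1:

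| Evaluable subjects | Escalate | Stay | De-escalate |
|---|---|---|---|
| 3 | 0 | 1 | 2 or more |
| 6 | 0–1 | none | 2 or more |
| 9 | 0–1 | 2 | 3 or more |
| 10 | 0–1 | 2–3 | 4 or more |

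The Amendment 1 log, used here only as context, lists "Revision of the targeted toxicity probability to 0.2". This confirms that 0.2 is the intended current target.

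**The concern.** A dose with a true DLT rate of 0.20 meets the target and is also classed as underdosed. The stay interval is centred on 0.30 and lies wholly above the target, and neither document explains why. It may be left over from a higher target, but that is an inference from its centre, not something the documents say.

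The escalation threshold therefore sits above the rate it is meant to protect, which raises the chance of moving up from a dose already at or above 0.2. The appendix intervals, the exclusion rule and the table also disagree with one another, so a reader cannot tell which of them produced the Part 1A decisions. At 1 DLT in 3 the table enrols more subjects at the dose, while the exclusion rule bars that dose and all higher ones for the rest of the trial.

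**Working it through.** **Inputs.** Target 0.2, intervals (0, 0.25), (0.25, 0.35) and (0.35, 1), prior Beta(1,1), 80% exclusion rule and 6-subject floor: Protocol Appendix 14 and SAP Appendix B. Looks at n = 3, 6, 9 and 10: Table 4-1. Assumption: the comparison interval is (0.15, 0.25), the target ± 0.05, which has the same width as the stated one.

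**Formulas.** With x DLTs in n, the posterior is Beta(1 + x, 1 + n − x). UPM of an interval = posterior probability of the interval ÷ its length. A dose is excluded if P(rate > 0.2) > 0.80.

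**The plan's own cell, 1 DLT in 6.** The posterior is Beta(2, 6).

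| Stay interval | UPM escalate | UPM stay | UPM de-escalate | Decision |
|---|---|---|---|---|
| (0.25, 0.35), as written | 2.220 | 2.111 | 0.360 | Escalate (agrees with Table 4-1) |
| (0.15, 0.25) | 1.889 | 2.716 | 0.593 | Stay |

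P(rate > 0.2) is 0.577, so the exclusion rule does not act here. With that rule applied to both versions, 1/6 is the only decision that differs at n = 3, 6, 9 and 10.

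**Sensitivity to width.** Every symmetric interval tried, from 0.2 ± 0.02 to 0.2 ± 0.10, gives stay at 1/6. From ± 0.06 upward, 1/9 becomes stay as well.

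**Probability of escalating from a dose.** Escalation counts only from n = 6, so 0/3 continues to 6. A stay at 10 counts as no escalation. De-escalation or exclusion ends the dose. At a true rate of 0.20:

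- P(0 in 6) = 0.8^6 = 0.2621. P(1 in 6) = 6 × 0.2 × 0.8^5 = 0.3932.
- P(0 in 3, then 1 in the next 3) = 0.512 × 0.384 = 0.1966. With the exclusion rule this is the only route to 1/6, because 1/3 is already excluded (0.819).
- As written, no exclusion rule: 0.2621 + 0.3932 = 0.655. With it: 0.2621 + 0.1966 = 0.459.
- Centred, no exclusion rule: 1/6 stays and escalates at 9 if the next 3 have no DLT, so 0.2621 + 0.3932 × 0.512 = 0.463. With it: 0.2621 + 0.1966 × 0.512 = 0.363.
- Half-width 0.06 or more: 1/9 also stays and needs one more DLT-free subject, so 0.2621 + 0.8 × 0.2013 = 0.423. With the exclusion rule: 0.2621 + 0.8 × 0.1007 = 0.343.

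| True DLT rate | As written, with 80% rule | (0.15, 0.25), with 80% rule | As written, without | (0.15, 0.25), without |
|---|---|---|---|---|
| 0.20 | 45.9% | 36.3% | 65.5% | 46.3% |
| 0.25 | 35.6% | 25.3% | 53.4% | 32.8% |
| 0.30 | 26.9% | 17.0% | 42.0% | 22.1% |

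With the same floor, Table 4-1 alone gives the same escalation probabilities as the written UPM rule alone.

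**Does the table follow from the written parameters?**

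- With the 80% rule it differs at 1/3 (P = 0.819) and 3/10 (P = 0.839): the table says stay, the rule says unacceptable.
- Without it, the table differs at 2/6, 3/6, 3/9, 4/9 and 4/10: the table says de-escalate, UPM says stay.

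**The case against.** The strongest reply has five parts.

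- **The study is over.** The SAP records early termination, and Part 2 did not enrol. No future escalation decision can change, and nothing shows that any cohort had 1 DLT in 6. This stands and limits the practical harm. It does not remove the need to say which rule was used, since the May 2024 SAP reprints the inconsistent rule and DLTs will be listed.
- **Escalating at 1/6 follows an observed rate of 16.7%, below target.** True, but under the stated prior the posterior mean at 1/6 is (1 + 1)/(2 + 6) = 0.25, above target.
- **The stay result depends on the comparator.** Partly true: (0.19, 0.42) contains 0.2 and still escalates at 1/6. That interval is wide and strongly asymmetric, and every symmetric interval tried gives stay.
- **The rule is only a guide.** Escalation needs a unanimous DLRT vote and a sponsor decision, and the Part 1B dose rests on an integrated review of safety, efficacy, PK and PD. The aim is a minimum safe and effective dose rather than an MTD. These safeguards limit the effect, but the team still receives an escalate signal at 1/6. Overshooting 0.2 also sits badly with a minimum-dose aim.
- **Centring has a price.** This stands. At a true rate of 0.15, below target, escalation falls from 57.7% to 50.0% with the 80% rule. Because cohorts are capped at 10, some of that is escalation lost rather than delayed.

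The larger contrast (65.5% against 46.3%) also leaves out a written rule. The figures with the exclusion rule describe the appendix as a whole.

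**Conclusion.** The concern holds. The stay interval excludes the stated target, and at the first sample size where escalation is allowed this turns 1 DLT in 6 from stay into escalate. Under the full written rule, the chance of escalating rises by 9.6 percentage points at a true DLT rate of 0.20 (45.9% against 36.3%), 10.3 at 0.25 and 9.9 at 0.30. By table or UPM alone the rise at 0.20 is 19.2 points. These sizes rest on the ± 0.05 comparison interval, the four looks and the 6-subject floor. The direction at 1/6 does not depend on the half-width within the symmetric range tried. Separately, the appendix intervals, the 80% rule and the table cannot all be in force together. Early closure lowers the practical harm but leaves the rule behind Part 1A undocumented.

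**What to change.** In Protocol Appendix 14 and SAP Appendix B, replace the stay interval with one centred on 0.2, for example (0.15, 0.25), or restate the target that the present intervals serve. An interval that merely contains 0.2 is not enough. Regenerate Table 4-1 and SAP "Table 3-1. Guidelines for Dose Level Decisions in Part 1" by code from that single parameter set, including the exclusion cut-off.

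Since the study has closed, the action that still matters is reporting. Add the discrepancy to SAP Section 10, which omits it although it already says "These changes will also be documented in the Clinical Study Report". Then state in that report whether the appendix intervals, the 80% rule or the table drove the Part 1A decisions. Section 10 is headed as changes from protocol-specified analyses, so the entry should make clear that it records an inconsistency carried over from the protocol.

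The cost is wording in two appendices, one regenerated table per document, one Section 10 item and one sentence in the report. No extra patients are needed. If the design is reused, the price is slower and sometimes forgone escalation from doses below the target.
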